July 19, 2024

Protocol:

**Retrospective study on anti-cancer systematic therapy for
gastric cancer patients complicated with bleeding**

Retrospective study on anti-cancer systematic therapy for gastric cancer patients complicated with bleeding

Abstract

BACKGROUND

Hemorrhage isn't a rare complication with gastric cancer (GC)/gastroesophageal junction cancer (GEJC) and may lead to poor prognosis.

AIM

To investigate the impact of overt bleeding (OB) on the survival and treatment related adverse events (TRAEs) of GC/GEJC patients.

METHODS

This study will retrospectively enroll advanced or metastatic GC/GEJC patients who received systematic treatment at Peking University Third Hospital. The study aims to investigate the impact of OB on TRAEs for GC/GEJC patients receiving anti-cancer treatment, evaluate the risk factors of overt bleeding after treatment (OBAT), assess the influence of overt bleeding on the overall survival (OS).

Key words: Gastric cancer (GC)/gastroesophageal junction cancer (GEJC), Overt bleeding (OB), Systematic treatment

INTRODUCTION

Gastric cancer was the fifth most common cancer and ranked fourth for cancer mortality worldwide in 2020[1]. Hemorrhage wasn't a rare complication with gastric cancer (GC)/gastroesophageal junction cancer (GEJC). About 15.7% of GC/GEJC patients experienced bleeding[2]. Hemorrhage not only reduced the quality of life in GC/GEJC patients, but also led to poor prognosis even life-threatening if it was failure to timely stop and affected anti-cancer treatment[3, 4].

Risk factors for hemorrhage with GC/GEJC were various, including oldness, smoking history, chronic disease, use of antithrombotic/anticoagulants and so on[2, 5]. Radical gastrectomy was an ideal for early stage GC/GEJC with overt bleeding (OB),

but there was no curable chance for patients with advanced or metastatic GC/GEJC and hemostatic strategies such as endoscopic therapy, transcatheter arterial embolization were prone to rebleeding[4, 6, 7]. GC/GEJC patients with hemorrhage were less likely to receive chemotherapy due to poor physical quality and concern about treatment related adverse events (TRAEs) and rebleeding.

The retrospective study aims to investigate the impact of OB on TRAEs for GC/GEJC patients receiving anti-cancer treatment, assess the influence of overt bleeding on the overall survival (mOS).

PATIENTS AND METHODS

Data source and study patients

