We will retrospectively enroll patients who were diagnosed with advanced or metastatic GC/GEJC at department of medical oncology and radiation sickness of Peking University third hospital. The eligibility criteria are as follows: 1) patients older than 18 years. 2) a histologically confirmed diagnosis of advanced or metastatic GC/GEJC. 3) the initial anti-cancer treatment was systematic therapy, including chemotherapy, targeted therapy or immune checkpoint inhibitor (ICI). 4) no history of gastrectomy before systematic therapy. The exclusion criteria included: 1) incompletable clinical data. 2) Siewert I type esophagus cancer.

The patients information collected from the database is as follows: age, gender, height, weight, Eastern Corporative Oncology Group Performance Status (ECOG-PS), chronic disease, drinking history, smoking history, diagnosis and metastatic sites, primary tumor location, histological grade, clinical stage according to the 8th edition of AJCC (American Joint Committee on Cancer) cancer staging manual, overt bleeding, symptoms, therapy strategy, tumor response to treatment, objective response rate (ORR), disease control rate (DCR), TRAEs and media overall survival (mOS).

Definitions

The diagnosis of OB is that the following conditions occurred one month before systematic treatment: 1) melena, hematemesis or hematochezia caused by gastric lesion, or 2) gastric hemorrhage confirmed by endoscopy. This study will only

analyze the impact of gastric overt bleeding (not including occult bleeding) on patients.

The radiographic best response to treatment will be assessed as complete response (CR), partial response (PR), stable disease (SD), no CR or no progressive disease (PD), or PD on the basis of response evaluation criteria in solid tumor 1.1 by clinicians. Objective response rate (ORR) is defined as the proportion of patients with the best response CR or PR. Disease control rate (DCR) is defined as the proportion of patients whose best response was CR, PR, no CR or no PD, or SD. Patients will be followed up at regular intervals. The criterion for terminating follow-up is death for any reason. OS is defined as the time from the first cycle of systematic therapy to death from any cause. TRAEs are evaluated according to the National Cancer Institute Common Toxicity Criteria version 4.0.

Statistical analysis

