We will use SPSS version 25.0 (International Business Machines, New York, United States) to analyze the data and considered that differences are statistically significant if the two-sided P values are less than 0.05. The classified variables will be assessed by the χ^2 test or Fisher's exact test. A binary logistic regression model (entry method) will be used to identify items independently associated with OBAT. Odds ratios (ORs) and 95% confidence intervals (CIs) will be calculated. Survival curves will be estimated by the Kaplan-Meier method with the log-rank test. Hazard ratios (HRs) and 95%CIs will be calculated using the Cox proportional hazards model, and a check on the assumption of proportional risk will be conducted.

CONCLUSION

In conclusion, this study aims to evaluate the efficacy and safety of systematic therapy on GC/GEJC patients with bleeding. We hope the study will provide basis for future prospective clinical trial.

Institutional review board statement: This study was approved by the Peking University Third Hospital Medical Science Research Ethics Committee (IRB00006761-M2023544).

Informed consent statement: A waiver of informed consent was granted by the Ethics Committee.

REFERENCES

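### The OBAT model has no short baseline item list, no limit tied to the event count and no sparse-data method, so a small cohort could give inflated or non-estimable odds ratios

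*Combined protocol and SAP*

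**What the plan says.** The Abstract names the evaluation of OBAT risk factors among the study's aims. The analysis for that aim, in the Statistical analysis section, is one sentence: "A binary logistic regression model (entry method) will be used to identify items independently associated with OBAT". It is followed by "Odds ratios (ORs) and 95% confidence intervals (CIs) will be calculated". The software statement is "We will use SPSS version 25.0", and the general rule is that "differences are statistically significant if the two-sided P values are less than 0.05". No adjustment for multiple testing is given.

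The items for this model are not named. The nearest thing to a list is the data-collection paragraph under Data source and study patients, which begins "The patients information collected from the database is as follows: age, gender, height, weight" and runs through performance status, habits, disease features, overt bleeding, symptoms and therapy. The same paragraph goes on to "tumor response to treatment, objective response rate (ORR), disease control rate (DCR), TRAEs". It does not say which of these variables enter the OBAT model.

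The documents give no cohort size, accrual window or expected OBAT count. The only bleeding frequency is in the Introduction: "About 15.7% of GC/GEJC patients experienced bleeding". That is a cited figure for bleeding in this cancer generally, not for OBAT. The Definitions section defines bleeding in the month before treatment but gives no definition or time window for OBAT.

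**The concern.** Maximum-likelihood odds ratios are biased away from 1 when there are few events per model parameter. When an item, or a combination of items, separates bleeders from non-bleeders perfectly, the estimate does not exist. The collection paragraph has 15 or 16 pre-treatment items, depending on whether diagnosis and metastatic sites count as one or two. Several are naturally multi-category, so the parameter count could be higher. The cohort comes from one hospital, patients with incomplete data are excluded, and OBAT may well be a minority event.

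Two further gaps sit beside this one. Each item is tested at 0.05 with no adjustment. And nothing confines the model to baseline data, although tumour response and TRAEs can follow, or result from, a bleed. The study is meant to inform a later prospective trial, so exaggerated or false risk factors could carry forward.

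**Working it through.** The plan has no figure to reproduce: cohort size, OBAT rate and target odds ratio are all unstated. The check is therefore a range under assumptions.

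**Events per parameter** = N × rate / number of parameters. Using the Introduction's 15.7% as a stand-in and 16 one-parameter items:
- N=100: 15.7/16 = 1.0
- N=200: 31.4/16 = 2.0
- N=500: 78.5/16 = 4.9
- N=1000: 157/16 = 9.8

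**Simulation A.** 1,500 cohorts per setting, 15 independent items (binary prevalence 15% to 50%, one continuous), one true odds ratio of 2, 14 null items, 15.7% event rate.

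**Simulation B.** 800 cohorts per setting (500 for Firth), 16 correlated binary items (prevalence 10% to 50%, latent correlation 0.15), two true odds ratios of 2, 14 null items.

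Maximum likelihood, all items entered. The mean is the exponential of the mean log odds ratio among fits that converged.

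| Simulation | N | Rate | Events | Mean OR (true 2) | Fit fails |
|---|---|---|---|---|---|
| A | 100 | 15.7% | 16 | 2.58 | 22% |
| A | 200 | 15.7% | 31 | 2.19 | 1.5% |
| A | 400 | 15.7% | 63 | 2.11 | 0% |
| B | 100 | 15.7% | 16 | 2.79 | 39% |
| B | 200 | 15.7% | 31 | 2.18 | 7.6% |
| B | 500 | 15.7% | 78 | 2.09 | 0.1% |
| B | 100 | 10% | 10 | not relied on | 71% |
| B | 200 | 10% | 20 | 2.39 | 24% |
| B | 500 | 10% | 50 | 2.11 | 0.9% |

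On the log scale the bias in B at 15.7% is ln 2.79/ln 2 − 1 = 48% at N=100 and ln 2.18/ln 2 − 1 = 12% at N=200. Among statistically significant estimates, the median odds ratio in B is 8.0, 3.2 and 2.3 at N=100, 200 and 500. Failure depends heavily on item prevalence: with evenly split items it falls below 1% at N=200 and 15.7%.

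**False factors.** For 14 independent null items, 1 − 0.95^14 = 51%. Simulation A gives 50% to 51%. Simulation B gives 45% to 59% in every setting except one with only 5 events (35%), and still 53% at N=500 with 125 events, where the log-scale bias is 2%. The error rate per null item is 3.6% to 6.4%, close to nominal. The cause is therefore the number of tests.

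**Separating the two remedies** (simulation B, 15.7% rate):
- *Firth, 16 items.* Mean odds ratio 1.98 at N=100 and 1.99 at N=200, with failure 0.4% and 0%. The chance of any false factor is 36%, 43% and 51% at N=100, 200 and 500, against 59%, 52% and 55% for maximum likelihood.
- *Maximum likelihood, 5 items.* Mean odds ratio 2.09 and 2.08 at N=100 and 200, with failure 3% and 0%. The chance of any false factor is 10% to 17% over the cohort sizes tried; with three null items the formula gives 1 − 0.95^3 = 14%.
- *Firth, 5 items.* Mean odds ratio 1.96 and 1.97, with no failures.

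With five items and only 10 events (N=100, 10% rate), maximum likelihood still fails in 12.8% of cohorts and Firth in none. A further comparison over N of 100 to 400, event rates of 10% to 30% and 6 or 15 items found Firth's root mean squared error never above that of maximum likelihood, with failures of 0% to 0.7% against up to 35%.

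**The case against.** A reader might infer that the plan's odds ratios will be exaggerated. The documents do not support that. Without a cohort size or an OBAT rate the event count is unknown, the 15.7% is not an OBAT rate, and with 50 or more events in 400 to 500 patients the distortion is slight. This objection stands, and the point is conditional.

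A reader might also infer that maximum likelihood or forced entry produces the spurious factors. It does not. Forced entry avoids data-driven selection, and the proposed fix also enters its items together. The figure of about half also assumes 14 null items. The Introduction names age, smoking and chronic disease as bleeding risk factors, so there may be fewer.

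The data-collection paragraph serves every aim and is not a model specification. A planned model of 15 or more items, or one containing response or TRAEs, would be an argument from silence. ORR and DCR are defined as proportions of patients and could not be patient-level covariates at all. What remains is that nothing in the plan rules out a long list, or patient-level response and TRAEs as items.

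Finally, shortening the list does most of the work, so Firth may look like a preference. That is largely fair at 30 or more events. It is less so near 10 events, where five-item maximum likelihood still fails in about one cohort in eight. Where events are plentiful Firth approaches maximum likelihood, so little is lost by adopting it in advance.

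**Conclusion.** The concern holds in conditional form, and the plan should be changed. The documents leave the OBAT items, their number, their timing and the handling of sparse data open. If the cohort is around 100 to 200 patients with a 10% to 16% event rate and about 15 items are entered, a true odds ratio of 2 would average about 2.1 to 2.8. Fit failure would range from under 1% to 71%, depending on item prevalence, correlation and event rate. At 400 to 500 patients with 50 or more events, neither matters much. The roughly 50% chance of a false independent factor is a separate multiplicity problem that remains at any cohort size if about 14 null items are tested unadjusted.

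All these figures rest on assumed cohort sizes, event rates, item counts and effects. Monte Carlo standard errors on proportions in simulation B reach about 1.8 points, and more where many fits failed. The events per parameter cannot be settled until OBAT is defined and the cohort counted.

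**What to change.** Amend the Statistical analysis section along these lines: OBAT will be modelled by Firth-penalised logistic regression, with all items entered together. Only items recorded before cycle 1 will be used, from a short list fixed before any association with OBAT is examined and drawn from data already collected (for example pre-treatment overt bleeding, age, smoking history, chronic disease and ECOG-PS). The number of model parameters will not exceed a stated fraction of the observed OBAT count. All other items will be reported descriptively.

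The limit must be a number. As an illustration only, one parameter per five events would allow 31/5 = 6 parameters at N=200 and 15.7/5 = 3 at N=100, using the 15.7% rate. In simulation B with five items and 25 events (N=100), Firth gave a mean odds ratio of 2.00 with no failures. Multi-category items must be counted by their parameters. Add antithrombotic use only if it can be abstracted from the records: the Introduction names it as a risk factor, but the collection paragraph does not list it.

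The cost is revised wording, a non-default routine (R or an SPSS extension) and no adjusted odds ratios for items outside the list. Abstracting antithrombotic use, if attempted, is extra work.
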